## **Material and methods**

### ***Study population:***

This study included 26 children with fulminant hepatitis A. They were recruited over a period of 4 years duration and divided into two groups. Group one is comprised of 18 children with fulminant HAV infection who received steroid therapy beside standard supportive measures (steroid group). The second group is comprised of 15 children with fulminant HAV infection who did not receive steroid therapy, but only standard supportive measures (non steroid group). All cases were recruited from the department of Pediatric Hepatology, Gastroenterology and Nutrition, National Liver Institute, Menofiya University. Those patients whose parents accepted to receive steroids were allocated in the steroids group; others were allocated in the control group. From each group a random sample was chosen using SPSS. An informed consent was signed by the parents of the steroid-treated patients before recruitment in the study which was approved by the Research Ethics Committee of National Liver Institute.

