### ***Outcome assessment***

The parameters of the primary response were improvement of PT followed by improvement of alanine transaminase and aspartate transaminase together with decreasing bilirubin during the period of observation. The overall clinical outcome (recovery or death) was

considered secondary response parameter. Treatment tolerability and side effects were also monitored.

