### ***Statistical analysis plan (SAP)***

Quantitative data were presented as mean  $\pm$  standard deviation (SD) while qualitative data were presented as number and percentage. For both homogenously distributed and non homogenously distributed quantitative data, significance was tested by either independent samples *t*-test or by Mann-Whitney U test, respectively. Chi-square test or Fisher's exact test was used for the measurement of the qualitative data significance. Significance was set at *P* value  $< 0.05$ . A stepwise regression analysis was performed to examine independent factors associated with the outcome. Standardized regression coefficient ( $\beta$ ), 95% confidence interval (CI) and *P* values of each independent factor are presented. Statistical analysis was performed using SPSS, version 13 (SPSS Inc, Chicago, IL, USA).

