## Results

**Table 1:** Outcome of steroid therapy

Characteristics	Steroid (n = 18)	Non-Steroid (n = 15)	P-value
Type of steroids			
Methylprednisolone	10 (55.6)	--	
Prednisolone	8 (44.4)	--	
Duration of steroids (days)			
Minimum-Maximum (median)	5 – 50 (22)	--	
Outcome			
Living	15 (83.3)	4 (26.7)	0.001
Dead	3 (16.7)	11 (73.3)	

[figure not shown]
Number of living patients were significantly higher in the steroid group compared to non-steroid group

**Table 2:** Stepwise regression analysis for parameters with significance between living and dead patients

Characteristics	$\beta$	P-value	95% CI	
			Lower	Upper
Steroid therapy	0.571	0.001	0.268	0.865
Prothrombin time (seconds)	NI	--	--	--

$\beta$ : regression coefficient; CI: confidence interval; NI: not included

Steroid therapy was the only independent parameter associated with survival of patients

**Figure 1.** Serial changes of prothrombin time (A) and total bilirubin (B) in the steroid group.

PT: prothrombin time

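### Table 2's independent steroid effect is the unadjusted survival difference between non-randomised groups, and it pairs a standardized coefficient with the unstandardized interval

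*Combined protocol and SAP*

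**What the plan says.** - **Allocation** (Study population): "Those patients whose parents accepted to receive steroids were allocated in the steroids group; others were allocated in the control group". The random sample drawn in SPSS was taken within each of these groups, after treatment had been decided, so it does not randomise treatment.
- **Number of patients** (Study population): "This study included 26 children with fulminant hepatitis A". The same paragraph gives groups of 18 and 15, which sum to 33. Tables 1 and 2 are consistent with 33.
- **Outcome** (Outcome assessment): recovery or death, a binary outcome, is the secondary response. Prothrombin time is part of the primary response.
- **Analysis** (SAP): "A stepwise regression analysis was performed to examine independent factors associated with the outcome". The section promises a "Standardized regression coefficient" with a 95% CI and P value for each factor. It gives no model type, candidate list, or entry or removal rule.
- **Result** (Table 2, titled "Stepwise regression analysis for parameters with significance between living and dead patients"): steroid therapy has β 0.571, P 0.001, 95% CI 0.268 to 0.865. Prothrombin time is marked NI. The footnote labels β only as "regression coefficient; CI: confidence interval; NI: not included".
- **Conclusion** (below Table 2): "Steroid therapy was the only independent parameter associated with survival of patients".

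**The concern.** Calling a factor *independent* tells the reader that its effect was estimated with other factors held constant. A final model with one term cannot show that. When a stepwise procedure leaves prothrombin time out, this shows only that it did not add significantly once steroid therapy was in. It does not give the steroid effect with prothrombin time held. With 33 patients and 14 deaths, failure to enter is weak evidence that a variable does not confound.

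The design does not make up for this. Families who accepted steroids may have had children who differed in severity from those who declined, and nothing in the allocation balances the groups.

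Survival is a secondary response, but Table 2 holds the only effect estimate with an interval in the text available for review, so the main survival claim rests on it. There is also a smaller reporting fault: the estimate and interval in the row are on different scales, and neither is labelled as a survival difference.

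**Working it through.** **Inputs** (Table 1): alive 15 of 18 on steroids and 4 of 15 without; in total 19 alive, 14 dead, n = 33.

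**1. Reproduce the printed interval with no covariate.** Least squares of survival (1/0) on steroid therapy (1/0):

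- B = 15/18 − 4/15 = 0.8333 − 0.2667 = 0.5667
- Residual sum of squares = 18(0.8333)(0.1667) + 15(0.2667)(0.7333) = 2.500 + 2.933 = 5.433
- Residual variance = 5.433/31 = 0.1753
- SE = √[0.1753 × (1/18 + 1/15)] = 0.1464
- 95% CI = 0.5667 ± 2.0395 × 0.1464 = **0.268 to 0.865**; P = 0.0005, which prints as 0.001

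This is Table 2's interval to three decimals. Residual degrees of freedom of 30 or 29 give 0.268 to 0.866 and 0.267 to 0.866. A Wald interval for the difference gives 0.284 to 0.849. Among all two-group tables with totals from 20 to 40 and a difference of 0.50 to 0.65, only 15/18 against 4/15 and its mirror coding as deaths give the printed limits. No split of 26 patients does.

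**2. Reproduce the printed β.** The standardized coefficient with one predictor is the phi correlation:

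- β = (15 × 11 − 3 × 4)/√(18 × 15 × 19 × 14) = 153/268.0 = **0.571**
- SD(steroid)/SD(survival) = √[(18 × 15)/(19 × 14)] = 1.0075
- SE of β = 0.1464 × 1.0075 = 0.1475
- 95% CI = 0.5709 ± 2.0395 × 0.1475 = 0.270 to 0.872

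| Quantity | Estimate | 95% CI |
|---|---|---|
| Printed in Table 2 | 0.571 | 0.268 to 0.865 |
| Unstandardized B (survival difference) | 0.567 | 0.268 to 0.865 |
| Standardized β | 0.571 | 0.270 to 0.872 |

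The printed row takes its estimate from the third line and its interval from the second. The midpoint of the printed interval is (0.268 + 0.865)/2 = 0.5665, which is B. The distances from 0.571 are 0.303 below and 0.294 above.

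**3. The same contrast by methods suited to small binary data (all unadjusted).**

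- Newcombe interval for the 56.7-point difference: 22.8 to 75.8 points. Against the printed limits this is 4.0 points lower at the bottom and 10.7 lower at the top. The shift comes from the interval method and not from the scale mismatch.
- Firth odds ratio for survival: (15.5 × 11.5)/(3.5 × 4.5) = 11.3, profile 95% CI 2.5 to 64.1
- Fisher's exact test: P = 0.0016

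**4. Sensitivity to non-random allocation.** The survival ratio is 0.8333/0.2667 = 3.125, 95% CI 1.3 to 7.4. The E-value is RR + √[RR(RR − 1)].

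- Estimate: 3.125 + √(3.125 × 2.125) = 5.7
- Lower limit (1.317): 1.317 + √(1.317 × 0.317) = 2.0

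A factor related to both allocation and survival by a risk ratio of about 2.0 each could bring the lower limit to 1. About 5.7 each would be needed to remove the estimate. Coded as death, the ratio is 4.4 and the E-values are 8.3 for the estimate and 2.4 for the limit nearer 1.

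An adjusted estimate cannot be computed here, because the documents give no patient-level covariates.

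**The case against.** The strongest reply is that the table already discloses the position. Prothrombin time was a candidate and is marked as not included, and *only independent parameter* is usual wording for the sole variable that a stepwise procedure keeps. The disclosure is real, but the sentence below the table still says more than a one-term model can, and in groups formed by parental choice the difference matters.

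Four further points have some force:

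- **The scale mismatch is a labelling slip.** Agreed. Printing 0.567 beside the existing interval would cure it.
- **The printed interval is a correct t interval for B, and nothing in the documents calls for Newcombe.** Agreed. Newcombe is a better choice for proportions in groups this small, but the printed limits are not an arithmetic error.
- **The SAP's reference to a standardized coefficient points to linear regression, and Table 2's title gives a screening rule.** Partly so. The model is still inferred rather than stated, and the entry and removal rule is not given.
- **A model with prothrombin time alone is thin.** Encephalopathy, part of the case definition, is left out, and that definition allows entry on INR, so baseline prothrombin time in seconds may be incomplete. These points limit what the refit can show. They are a reason to report it as post hoc and not to call its result independent. Table 2 lists prothrombin time in seconds, so the variable was analysed.

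The E-values depend on coding survival or death, but under either coding the conclusion is the same.

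**Conclusion.** The concern holds. Table 2 restates Table 1's crude difference of 56.7 percentage points and adds no control for confounding, so *independent* is not supported. The row also mixes scales, by 0.004 in the estimate and by 0.002 and 0.007 in the limits, with no effect on significance. This should be fixed: the association is strong and remains significant, but the wording claims more than the analysis shows.

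The conclusion assumes 33 patients analysed (not 26) and two-sided 95% intervals. Linear regression is inferred from the three-decimal match and needs the analysts' confirmation. No claim is made that the association is false or that a baseline comparison is absent from the study.

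**What to change.** 1. **Table 2.** Replace the row with the unadjusted survival difference, 56.7 percentage points (Newcombe 95% CI 22.8 to 75.8). Drop the standardized coefficient from the table and footnote, and align the SAP with this.
2. **SAP.** State the model actually used (linear regression, if the analysts confirm it), the candidate variables and the entry and removal rule.
3. **Added analysis, marked post hoc.** Fit one Firth logistic regression with steroid therapy and baseline prothrombin time both kept in. Report the odds ratio and its profile 95% CI whatever the result, and the number of patients with a baseline value. The baseline value is needed because prothrombin time is also a primary response and Table 2 gives no time point. Note that the odds ratio is not a survival ratio (crude ratio 3.1).
4. **Sentence below Table 2.** Remove *independent*. If the post hoc model supports it, say that steroid therapy was associated with survival after adjustment for baseline prothrombin time, and that allocation followed parental acceptance and was not randomised. If it does not, report the unadjusted association with the same caveat.

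**Cost.** A re-run on existing records and some rewording; no new data, provided baseline prothrombin time is on file. Both limits of the survival difference move down because of the interval method. With 14 deaths and two predictors (7 deaths per predictor) the adjusted estimate will be imprecise and could weaken the claim. Being post hoc, it carries less weight than a planned analysis.

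### The regression planned for recovery or death has no named model and a standardised coefficient; Table 2 matches a linear fit and pairs that coefficient with the unstandardised slope's interval

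*Combined protocol and SAP*

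**What the plan says.** The section headed Statistical analysis plan (SAP) gives chi-square or Fisher's exact tests for qualitative data and then adds: "A stepwise regression analysis was performed to examine independent factors associated with the outcome". It does not say whether the regression is linear or logistic, and it gives no candidate list and no entry or removal limits. The quantity to be reported is a "Standardized regression coefficient" with a 95% confidence interval and a P value, and these "of each independent factor are presented".

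The outcome is binary. Outcome assessment introduces it as "The overall clinical outcome (recovery or death) was" a secondary response. Improvement of prothrombin time is listed in the same section among the primary response parameters.

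In Results, Table 2 is titled "Stepwise regression analysis for parameters with significance between living and dead patients". For steroid therapy it prints β 0.571, P 0.001 and 95% CI 0.268 to 0.865; prothrombin time is marked as not included. The footnote defines β only as "regression coefficient; CI: confidence interval; NI: not included", without the word standardised. The conclusion drawn is: "Steroid therapy was the only independent parameter associated with survival of patients".

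**The concern.** A standardised coefficient belongs to linear regression and does not express a survival benefit. With one binary predictor and one binary outcome it equals the phi correlation. A reader of Table 2 could take 0.571 for a difference in survival probability or a log odds ratio, and it is neither.

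The printed interval is also not centred on the printed estimate. The SAP calls the coefficient standardised, the table footnote does not, and the scale of the interval is stated nowhere.

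Table 2 is the only support shown in the available text for the statement of independence. The comparison is not randomised: "Those patients whose parents accepted to receive steroids were allocated in the steroids group". The adjusted analysis therefore carries weight, and its model should be named and suited to the outcome.

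**Working it through.** **Inputs.** Table 1: steroid 15 alive and 3 dead (n = 18); non-steroid 4 alive and 11 dead (n = 15). Total 33, with 19 alive and 14 dead. (Study population gives 26 children, but its groups of 18 and 15 sum to 33; Table 2 reproduces on 33.) Because prothrombin time was not retained, the final model contains steroid only and these counts are enough to rebuild it.

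**1. Linear regression of survival (0/1) on steroid (0/1).**
- Slope = 15/18 − 4/15 = 0.8333 − 0.2667 = 0.5667.
- Residual sum of squares = 18(0.8333)(0.1667) + 15(0.2667)(0.7333) = 2.500 + 2.933 = 5.433. Divided by 31 df: 0.1753.
- Sum of squares of the predictor = 18 × 15/33 = 8.182.
- SE = √(0.1753/8.182) = 0.1464.
- 95% CI = 0.5667 ± 2.0395 × 0.1464 = 0.2682 to 0.8652, the printed 0.268 to 0.865.
- t = 0.5667/0.1464 = 3.87, P = 0.00052, consistent with the printed 0.001.

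**2. Standardised beta (phi).**
- Phi = (15 × 11 − 3 × 4)/√(18 × 15 × 19 × 14) = 153/267.99 = 0.5709, the printed 0.571.
- SD ratio = √[(18 × 15)/(19 × 14)] = 1.0075. Multiplying the slope's limits by it gives the matching interval, 0.270 to 0.872.

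**3. Could rounding explain the pairing?** The midpoint of the printed limits lies between (0.2675 + 0.8645)/2 = 0.5660 and (0.2685 + 0.8655)/2 = 0.5670. That contains the slope and excludes 0.571.

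**4. Could another method give the printed interval?** None of those tried does:

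| Method | 95% interval |
|---|---|
| Standardised linear fit | 0.270 to 0.872 |
| Fisher-z interval for phi | 0.283 to 0.764 |
| Robust errors, HC0 | 0.273 to 0.860 |
| Robust errors, HC1 | 0.264 to 0.870 |
| Robust errors, HC2 | 0.263 to 0.870 |
| Robust errors, HC3 | 0.253 to 0.880 |
| Wald risk difference | 0.284 to 0.849 |
| Logistic log odds ratio | 0.934 to 4.308 |

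**5. Measures suited to a binary outcome, same counts.**
- Odds ratio = (15 × 11)/(3 × 4) = 13.75. Log OR = 2.621, SE = √(1/15 + 1/3 + 1/4 + 1/11) = 0.861. 95% CI 2.54 to 74.3, Wald P = 0.0023.
- Fisher's exact P = 0.0016.
- Firth OR 11.3 (2.53 to 64.1); exact conditional OR 12.4 (2.04 to 106).
- Risk difference 0.567 with Newcombe interval. The Wilson limits are 0.608 to 0.942 (15/18) and 0.109 to 0.520 (4/15). Lower = 0.567 − √[(0.833 − 0.608)² + (0.520 − 0.267)²] = 0.228. Upper = 0.567 + √[(0.942 − 0.833)² + (0.267 − 0.109)²] = 0.758. Against the linear interval, the lower limit falls by 0.040 and the upper by 0.107.

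**The case against.** **The scale mismatch is trivial.** It is 0.004 in the estimate and at most 0.007 in the limits, and a footnote would cure it. This stands. The mismatch matters mainly as evidence of which model was run; the model choice is the substantive point.

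**Phi depends on the group split.** A reader might infer that the split has materially distorted the printed coefficient. The documents do not support that. With survival held at 83.3% v 26.7% and N = 33, beta is 0.571 at 18:15, 0.568 at both 16:17 and 20:13, and 0.564 at 21:12. Large shifts need hypothetical splits far from the actual one. Nor was the split set by parental choice alone: Study population says a random sample was then drawn from each group. The dependence is a reason of principle for not reporting phi; it is not a source of error of any size here.

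**The conclusion does not change.** Crude significance holds under every test above. A reader might infer that the steroid finding is reversed or that the statement of independence is false. Neither follows. Individual prothrombin values are not in the documents, so the adjusted logistic result cannot be computed.

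**A two-factor logistic model is fragile too.** With 14 deaths there are 7 per factor, and non-random allocation remains the larger threat to a claim of independence. Both remarks stand; they limit what a refit can deliver but do not justify the linear model.

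**Conclusion.** The point holds in a limited form. The SAP does not name the regression model and asks for a standardised coefficient for a binary outcome. Table 2 is matched to three decimals by ordinary linear regression, with the standardised beta (0.571) set beside the interval of the unstandardised slope (0.567; 0.268 to 0.865), and the table labels neither scale.

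The main consequence is that the reported coefficient is a correlation, not a survival effect, and that its interval comes from a method poorly suited to 33 binary outcomes. On the risk-difference scale, the change of interval method moves the upper limit from 0.865 to 0.758 and the lower from 0.268 to 0.228. Crude significance is unaffected. Whether steroid therapy remains the only independent factor in a logistic model with prothrombin time is open.

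This rests on two assumptions: that the fitted model contained steroid alone, as Table 2 shows, and that it used the 33 children of Table 1. The documents do not name linear regression; it is inferred from the agreement of the estimate and both limits. The correction is worth making but does not overturn the crude result.

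**What to change.** Label the change as a post hoc correction, since results are already reported.

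1. **SAP.** Replace the standardised coefficient with wording such as: Survival (recovery v death) is analysed by logistic regression; the odds ratio, 95% CI and P value of each factor are presented; Firth or exact logistic regression is used if separation occurs. The filled crude cells do not rule out separation once prothrombin time is added.
2. **Covariates.** Enter steroid therapy and pre-treatment prothrombin time together, without stepwise selection. State the time of measurement, because later prothrombin time is itself a response. Say that, as the Table 2 title indicates, its candidates were those that differed significantly between living and dead in the same patients; do not present them as prespecified.
3. **Crude effect.** Report the risk difference of 0.567 with its Newcombe interval, 0.228 to 0.758.
4. **Table 2.** Put estimate, interval and label on one scale, name survival as the outcome, and re-check the statement of independence after the refit.

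The cost is revised SAP wording, one re-run on existing data and a corrected table. The results will look less precise: the crude odds-ratio interval already runs from 2.54 to 74.3, and with 14 deaths the adjusted estimate will also be imprecise. None of this cures the non-random allocation by parental acceptance.

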## Results

**Table 1:** Outcome of steroid therapy

Characteristics	Steroid (n = 18)	Non-Steroid (n = 15)	P-value
Type of steroids			
Methylprednisolone	10 (55.6)	--	
Prednisolone	8 (44.4)	--	
Duration of steroids (days)			
Minimum-Maximum (median)	5 – 50 (22)	--	
Outcome			
Living	15 (83.3)	4 (26.7)	0.001
Dead	3 (16.7)	11 (73.3)	

[figure not shown]
Number of living patients were significantly higher in the steroid group compared to non-steroid group

**Table 2:** Stepwise regression analysis for parameters with significance between living and dead patients

Characteristics	$\beta$	P-value	95% CI	
			Lower	Upper
Steroid therapy	0.571	0.001	0.268	0.865
Prothrombin time (seconds)	NI	--	--	--

$\beta$ : regression coefficient; CI: confidence interval; NI: not included

Steroid therapy was the only independent parameter associated with survival of patients

**Figure 1.** Serial changes of prothrombin time (A) and total bilirubin (B) in the steroid group.

PT: prothrombin time

